#### **5.1.7.2 Hospitalization Procedures**

For patients requiring hospitalization, hospitalization will begin the evening before the first dose of venetoclax and continue for 24 hours after. Upon admission, serum chemistry and hematology laboratory samples should be drawn and IV hydration should be started with a target of 150–200 cc/hr or as clinically appropriate. Laboratory results should be reviewed, and electrolyte values should not demonstrate clinically significant abnormalities before the first dose of venetoclax; otherwise, the patient should receive additional prophylactic treatment and hydration before the initiation of dosing. A nephrology (or acute dialysis) service must be consulted/contacted on hospital admission (per institutional standards) to ensure emergency dialysis is available and the appropriate staff is aware and prepared to handle any necessary intervention for TLS. Telemetry should also be considered.

Serial vital signs will be measured and TLS laboratory samples will be drawn (serum chemistry as defined in Section 4.5.6) before the first dose administration of venetoclax and 8, 12, and 24 hour post-dose. In addition, hematology samples will be drawn 8 and 24 hours post-dose (see [Appendix 1](#) and [Appendix 2](#)). Samples are to be sent immediately to the laboratory and the investigator or designee must review the results promptly. Laboratory values obtained before the dose of venetoclax are to be used to determine whether a patient developed a change related to TLS. Laboratory results obtained 24 hours post-dose must be reviewed before administration of the dose of venetoclax on that day. Patients who develop electrolyte changes suggestive of TLS should undergo aggressive management and further monitoring according to the guidance in [Appendix 12](#).

For patients assessed by the investigator to be at particularly high risk of TLS may, in addition to hospitalization, the investigator after discussion with the Medical Monitor may stagger the dosing of venetoclax (venetoclax dosing may be initiated 2 or 3 days after the first idasanutlin dose during the first cycle of therapy), or start the patient at a lower dose of venetoclax and reach the specified dose in a step-wise fashion.

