#### **4.5.6 Laboratory, Biomarker, and Other Biological Samples**

##### **Local Laboratory Assessments**

Samples for the following laboratory tests will be analyzed at the study site's local laboratory for analysis:

- Hematology: hemoglobin, hematocrit, platelet count, RBC count, WBC count, percent or absolute WBC differential count (neutrophils, eosinophils, basophils, monocytes, lymphocytes, and other cells)
- Chemistry panel (serum or plasma): sodium, potassium, glucose, BUN or urea, creatinine, calculated creatinine clearance, calcium, total bilirubin, direct bilirubin, total protein, albumin, ALT, AST, alkaline phosphatase, amylase, lipase, LDH, and uric acid
- $\beta_2$  microglobulin
- Coagulation: INR, aPTT (or PTT), and PT
- Pregnancy test

All women of childbearing potential will have a serum pregnancy test at screening (within 7 days of Day 1 of Cycle 1). Because of the suspected effect idasanutlin on embryo-fetal development, monthly pregnancy testing is strongly recommended for women of childbearing potential.

- Viral serology
  - Hepatitis B testing includes HBsAg and total HBcAb.
  - Hepatitis C testing includes HCV antibody.
- Quantitative immunoglobulins: IgA, IgG, and IgM
- Bone marrow assessment

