#### **5.1.3.5 Electrolyte Disorders**

Electrolyte disorders (hypercalcaemia, hyperkalaemia, hyponatraemia, hypocalcaemia, hypokalaemia, hypomagnesaemia, hyponatremia, hyperphosphataemia, and hypophosphataemia) were commonly observed in patients treated with idasanutlin. In addition to institutional guidelines, electrolytes should be monitored during the treatment phase. Electrolyte disorders should be treated according to institutional guidelines.

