#### **5.1.6 Prophylaxis and Monitoring for Tumor Lysis Syndrome**

TLS is a risk for patients with NHL who are treated with high cell-killing agents, including venetoclax. Changes in blood chemistries consistent with TLS that require prompt management can occur as early as 6 to 8 hours following the first dose of venetoclax. The risk of TLS is a continuum based on multiple factors, including tumor burden and comorbidities. Risk is highest for patients with bulky disease, elevated leukocyte count, elevated pretreatment LDH levels, compromised renal function, and dehydration. Assessment of tumor burden with CT scan and CBC with WBC differential, as well as blood chemistry (potassium, uric acid, phosphorus, calcium, and creatinine), should be performed in all patients and correct preexisting chemistry abnormalities prior to initiation of treatment with venetoclax.

All patients must receive prophylaxis for TLS before the initiation of the first dose of venetoclax (see also Section 4.3.2.5). Prophylaxis will include the following:

- Appropriate hydration, consisting of a fluid intake of approximately 2–3 L/day starting 24–48 hours before the start of treatment
- Administration of an agent to reduce uric acid (such as allopurinol 300 mg/day orally beginning 72 hours before dose and continuing for 3–7 days afterwards) or

rasburicase IV (for those high risk patients with elevated uric acid levels before treatment, or when otherwise judged to be appropriate by the investigator) until normalization of serum uric acid and other laboratory evidence of TLS (e.g., elevated serum LDH levels)

- Laboratory results should be reviewed and electrolyte values should not demonstrate any clinically significant abnormalities before the first dose of venetoclax, or the patient should receive additional prophylactic treatment and hydration before the initiation of dosing
- Patient at higher risk of TLS will be hospitalized for the initial venetoclax dose. Patients not considered at higher risk of TLS may be hospitalized after discussion with the investigator and Medical Monitor

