On the day of the initial visit with administration of venetoclax (Day 1 of Cycle 1), serial vital signs, serum chemistry, and hematology samples will be drawn before the dose of venetoclax and 8 and 24 hours following the dose (see [Appendix 1](#) and [Appendix 2](#)). These samples are to be sent immediately to the laboratory and the investigator or designee must review the results promptly. Laboratory values obtained prior to venetoclax dosing are to be used to determine whether a patient developed a change related to TLS. Laboratory results obtained 24 hours post-dose must be reviewed before receiving the dose of venetoclax on that day. Patients who develop electrolyte changes suggestive of TLS should undergo aggressive management and further monitoring according to the guidance in [Appendix 12](#), Recommendations for Initial Management of Electrolyte Imbalances and Prevention of Tumor Lysis Syndrome.

In addition, if TLS is observed in the initial cohorts, staggering the dosing of venetoclax may be explored (venetoclax dosing may be initiated 2 or 3 days after the first idasanutlin dose during the first cycle of therapy), or starting at a lower dose of venetoclax and reaching the specified dose in a step-wise fashion after discussion with the Medical Monitor to prevent or promptly treat TLS.

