- e Patients who complete treatment or discontinue treatment for reasons other than disease progression will undergo assessments every 3 months during the post-treatment FU period, which will continue until disease progression, the start of new anti-lymphoma treatment, or the end of the study, whichever occurs first. The first post-treatment FU visit is 3 months after the EOI visit for patients who do not receive maintenance treatment and 3 months after the last dose for patients who receive maintenance treatment. Patients who experience disease progression or start another anti-lymphoma treatment will be evaluated for survival status and new anti-lymphoma treatment every 3 months during the survival follow-up period, which will continue until the end of the study. The end of the study is defined as the time when all enrolled FL patients have completed or discontinued study treatment and all enrolled DLBCL patients have been followed for at least 1 year after they have completed or discontinued study treatment.
- f Informed consent must be documented before any study-specific screening procedure is performed.
- g Vital signs include respiratory rate, pulse rate, body temperature, and systolic and diastolic blood pressures while the patient is in a seated position. For obinutuzumab infusions: For the first cycle and for patients who experience an infusion-related reaction, vital signs will be measured prior to the infusion, every 15 ( $\pm$ 5) minutes for the first 90 minutes of the infusion, and then every 30 ( $\pm$ 10) minutes until 1 hour after completion of the infusion. For the second and subsequent cycles, vital signs will be measured every 30 minutes during the infusion, except for patients who have experienced an infusion-related reaction during a prior infusion. For venetoclax, serial vital signs will be measured and TLS laboratory samples will be drawn (serum chemistry as defined in Section 4.5.6) prior to the first dose of venetoclax and 8, 12, and 24 hour post-dose.
- h Perform only for patients who will not be receiving maintenance treatment.

## Appendix 1

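### The scheduled post-dose TLS samples omit phosphorus, so Appendix 12's hyperphosphatemia hold rule has no input at the 24-hour review

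*Protocol*

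**What the plan says.** Protocol Section 5.1.7.2, for hospitalized patients, states that "TLS laboratory samples will be drawn (serum chemistry as defined in Section 4.5.6) before the first dose administration of venetoclax", with further draws 8, 12 and 24 hours after the dose. Appendix 1 footnote g (FL schedule) repeats the definition: "serum chemistry as defined in Section 4.5.6) prior to the first dose of venetoclax". Section 5.1.6 and footnote q of Appendices 1 and 2 require chemistry before the dose and at 8 and 24 hours, without naming analytes.

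The Section 4.5.6 chemistry list starts with sodium and potassium and ends with "alkaline phosphatase, amylase, lipase, LDH, and uric acid". Phosphorus is not on it. Footnote s of Appendices 1 and 2 gives the same list.

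Section 5.1.6 does name phosphorus, but in the work-up before venetoclax is started: "potassium, uric acid, phosphorus, calcium, and creatinine". For the day after the first dose it says: "Laboratory results obtained 24 hours post-dose must be reviewed before receiving the dose of venetoclax on that day".

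Two appendices rely on phosphorus. Appendix 5 counts a value above 4.5 mg/dL as one of four laboratory TLS criteria, of which two are needed. Appendix 12 acts on a value of at least 5.0 mg/dL that has risen by at least 0.5 mg/dL. The patient is hospitalized, a binder is given, nephrology is notified, and no more venetoclax is given until resolution.

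**The concern.** Appendix 12 sets a safety rule whose input the sampling schedule does not collect. The rise criterion compares a pre-dose with a post-dose value. Section 5.1.6 supplies the first, and nothing in the schedule supplies the second.

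The 24-hour review is the check before the second venetoclax dose. If a site follows the schedule exactly, isolated hyperphosphatemia in a patient with no symptoms and no other Appendix 12 trigger is invisible at that review, and dosing continues where Appendix 12 would stop it.

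There is also a recognition problem. TLS of any grade is an adverse event of special interest (Section 5.2.3), and SAP Section 6.2.2 identifies it by preferred term alone. A case that the investigator does not recognise is therefore not recovered from laboratory data.

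The omission extends beyond the first dose. Section 5.1.3.5 lists phosphate disorders among the electrolyte abnormalities: "hyperphosphataemia, and hypophosphataemia) were commonly observed in patients treated with idasanutlin". It asks that "electrolytes should be monitored during the treatment phase". The listed panel cannot show a phosphate disorder in either direction.

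**Working it through.** No sample size, power or error rate is involved. The check compares the analytes that the TLS rules need with the analytes that are scheduled.

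**Step 1: count the panel.** Grouped by type, the Section 4.5.6 list holds:
- 3 electrolytes: calcium, potassium, sodium
- 4 renal or purine items: uric acid, creatinine, its calculated clearance, urea (or BUN)
- 5 liver items: AST, ALT, alkaline phosphatase, bilirubin direct and total
- 2 proteins: albumin, total protein
- 4 others: LDH, lipase, amylase, glucose

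3 + 4 + 5 + 2 + 4 = 18 items, none of them phosphorus.

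**Step 2: compare it with each TLS rule.**

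| Source | Needed | On the panel | Missing |
|---|---|---|---|
| Section 5.1.6 pre-dose chemistry | 5 (potassium, uric acid, phosphorus, calcium, creatinine) | 4 | phosphorus |
| Appendix 5 laboratory criteria | 4 (uric acid, phosphorus, potassium, calcium) | 3 | phosphorus |
| Appendix 12 abnormality groups | 5 (potassium, uric acid, calcium, phosphorus, creatinine) | 4 | phosphorus |

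**Step 3: count scheduled post-dose phosphorus values before the second dose.**
- Section 5.1.6 and footnote q, 8 and 24 hours: 0 of 2.
- Section 5.1.7.2 and Appendix 1 footnote g, 8, 12 and 24 hours: 0 of 3.

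**Step 4: find where a post-dose phosphorus is ordered.** Appendix 12 includes it in rechecks after a potassium, uric acid or creatinine trigger, after symptomatic low calcium, or after a clinical feature of TLS. Each recheck depends on some other finding.

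**Step 5: illustrate with assumed values.** Let phosphorus be 4.0 mg/dL before the dose and 5.2 mg/dL at 24 hours, with potassium, uric acid, calcium and creatinine unchanged and no symptoms.
- Level: 5.2 ≥ 5.0, met.
- Rise: 5.2 − 4.0 = 1.2 ≥ 0.5, met.

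Appendix 12 would hold venetoclax. The scheduled report shows nothing abnormal.

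**Step 6: laboratory TLS.** Isolated hyperphosphatemia is one criterion and does not make laboratory TLS. Phosphorus can pair with uric acid, potassium or calcium. A uric acid or potassium value beyond its Appendix 5 limit also crosses an Appendix 12 trigger, and the recheck then includes phosphorus. That leaves phosphorus with low calcium and no symptoms, because the Appendix 12 calcium row requires symptoms. The low calcium is visible, and Section 5.1.6 should prompt a response to it: "Patients who develop electrolyte changes suggestive of TLS should undergo aggressive management and further monitoring". The second criterion still cannot be confirmed without a phosphorus value.

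**The case against.** The strongest reply is that the protocol's intent is clear. Section 5.1.6 names phosphorus at baseline and says that pre-dose values are used to judge whether a TLS-related change has occurred. Section 5.1.3.5 asks for electrolyte monitoring. A site that has measured a baseline phosphorus could reasonably repeat it. This is true, but Section 5.1.3.5 gives neither an analyte list nor a time point, and the baseline instruction covers only the work-up before venetoclax. The hold rule would then depend on local habit.

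Second, other triggers will often bring a phosphorus value. Infusion reactions on Cycle 1 Day 1 produce symptoms that prompt rechecks, and Appendix 12's clinical features include nausea, vomiting and diarrhea. Table 13 gives idasanutlin monotherapy rates of 68%, 50% and 68% for these; they are whole-study figures, not 24-hour ones. This narrows the gap but leaves the asymptomatic patient uncovered. Gastrointestinal triggers apply in both regimens. Regimen B is somewhat more exposed because venetoclax starts in Cycle 2, and Section 5.1.1.1 says infusion reactions fall substantially after the first infusion.

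Third, the expected risk is low. Section 5.1.4.1 describes phosphate rises in NHL as few and marginal. Section 3.3.2.3 reports initial venetoclax doses up to 400 mg in NHL without clinically significant TLS, and this trial starts at 200 mg with mandatory prophylaxis. That stands, and it limits the severity. It does not make the schedule consistent with the rule.

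Fourth, isolated hyperphosphatemia is not TLS. That also stands: the recognition point is confined to phosphorus with asymptomatic low calcium.

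**Conclusion.** The concern holds and should be fixed. The scheduled post-dose TLS samples cover 4 of the 5 Appendix 12 abnormality groups, and the missing one is phosphorus, at every scheduled post-dose time. The hyperphosphatemia hold rule therefore cannot be applied before the second venetoclax dose to an asymptomatic patient with no other trigger.

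This assumes that sites follow the schedule as written and do not add phosphorus themselves. The figures are counts of listed tests, not event rates, and the documents do not allow missed cases to be estimated. No effect on dose-limiting toxicities or on the dose-escalation model is claimed; Section 3.1.2.1 already exempts Grade 3 laboratory TLS without clinical manifestations.

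**What to change.** Add phosphorus to the Section 4.5.6 chemistry panel and to footnote s of Appendices 1 and 2, so that it is measured before the dose and at every scheduled post-dose TLS time point. The minimum alternative is to add it to the TLS draws in Sections 5.1.6 and 5.1.7.2 and in Appendix 1 footnote g. Changing the panel is better because Section 5.1.3.5 asks for electrolyte monitoring during the treatment phase. The cost is one analyte on tubes already drawn, plus the wording changes.

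A secondary correction concerns Regimen B. Section 5.1.6 and Appendix 1 footnote q tie TLS sampling to Cycle 1 Day 1, but venetoclax starts there on Cycle 2 Day 1. Add the day of the first venetoclax dose as a TLS sampling day and keep the Cycle 1 Day 1 draws for obinutuzumab. Footnote g already requires TLS chemistry at the first venetoclax dose, so the added sampling is hematology at 8 and 24 hours on Cycle 2 Day 1.

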#### **5.1.8 Management of Patients Who Experience Specific Adverse Events**

Patients should be assessed clinically before each study treatment administration.

Guidelines for management of toxicities are based on laboratory values obtained within 48 hours prior to Day 1 of each scheduled drug administration or within 24 hours prior to Days 8 and 15 of Cycle 1. Dosing will occur only if a patient's clinical assessment and laboratory test values are acceptable.

During induction, study treatment may be delayed for toxicity for a maximum of 21 days. If study treatment is delayed for more than 21 days, obinutuzumab or rituximab, idasanutlin, and venetoclax treatment will be permanently discontinued (see [Table 18](#)).

There will be no dose reductions of obinutuzumab or rituximab. Treatment delays apply to all toxicities described below; dose modifications apply only to toxicities that are considered to be related to either idasanutlin and/or venetoclax. The dose of idasanutlin may be reduced as outlined in [Table 15](#). The dose of venetoclax may also be reduced.

In parallel cohorts, in which one drug only is escalated, the dose of that drug can be reduced only once per treatment cycle. In diagonal cohorts, in which the doses of both drugs have been escalated, the dose of both drugs will be reduced once per treatment cycle. There will be no more than one dose reduction per treatment cycle. If the doses of idasanutlin and venetoclax are reduced, re-escalation is not permitted.

**Table 15 Idasanutlin Dose-Reduction Steps**

Initial Dose	Dose Reduction in Milligrams		
	Step 1	Step 2	Step 3
100 mg	Minus 50 mg	No further reduction a	No further reduction a
150 mg	Minus 50 mg	No further reduction a	No further reduction a
200 mg	Minus 50 mg	Minus 50 mg	No further reduction a
250 mg	Minus 100 mg	Minus 50 mg	No further reduction a
300 mg	Minus 100 mg	Minus 50 mg	Minus 50 mg
350 mg	Minus 100 mg	Minus 100 mg	Minus 50 mg
400 mg	Minus 100 mg	Minus 100 mg	Minus 50 mg

a When no further idasanutlin dose reduction is possible, the patient will be discontinued from the study.

The dose of venetoclax will be reduced by at least 25% from the current dose (rounded to the lower closest 50 mg) or return to the previous dose, with a minimum final dose of 200 mg. If the dose level reaches 200 mg, no further reduction will be allowed and the patient will be discontinued from the study.

Toxicities that occur during the cycle and subside prior to the next cycle should not trigger the suggested dose modifications. Guidelines for management of toxicities during induction treatment are provided in Section 5.1.8.1 and during consolidation or maintenance treatment in Section 5.1.8.2.

